5.5.3.3.3 TG02 or TMZ Hematological Adverse Events

The actions to be taken with TG02 or TMZ for hematological AEs in this study are based on these adverse event profiles. Hematological AEs should be managed as outlined in the table below and per local practice, where noted.

NOTE: * in below tables: There will be no dose reductions below 100 mg BIW

Group B: TG02-related Hematological Adverse Events

Adverse Event	Action to be taken with TG02/ TMZ
Thrombocytopenia	
Administration of TMZ or TG02 may induce thrombocytopenia. The profile of thrombocytopenia is different between TMZ and TG02. For TMZ, a nadir occurs around day 21. In a Phase 1b study of TG02 in combination with carfilzomib in multiple myeloma patients, 21% of patients administered TG02 at 250 mg bi-weekly experienced grade 3 or 4 thrombocytopenia. Onset was typically within the first week of administration and resolved within 72 hours after TG02 interruption. Attributing hematological and biochemical toxicity to TMZ versus TG02 may be challenging, This remains to be judged by the investigator, but guidance will be provided by the study chairs and Sponsor on an individual case-by-case basis.	
First occurrence of grade 3 event without bleeding	Skip one or more doses of TG02 and interrupt TMZ until improved to grade ≤1. Re-introduce TG02 and TMZ at initial dose.

Adverse Event	Action to be taken with TG02/ TMZ
Recurrence of the same grade 3 event without bleeding	
Skip one or more doses of TG02 and interrupt TMZ until improved to grade ≤ 1. Re-introduce TG02 at a reduced dose * and TMZ at a reduced dose.
 
If TG02/TMZ have been re-introduced after a second event and the event recurs, consider the individual benefit versus the risk of continuing TG02 or TMZ:
 
 • Discontinue TMZ. Continue TG02 at the same or a reduced dose * bi-weekly (on Days 1, 4, 8, 11, 15, 18, 22, 25) of a 28-day schedule. • Alternatively, discontinue TG02 and continue TMZ at a reduced dose 
If TG02 or TMZ has been re-introduced after a third event and the event recurs, discontinue TG02 and TMZ.

First occurrence of grade 3 with bleeding or grade 4 event occurring on Day -7 to Day -1 prior to Cycle 1 Day 1	
Skip one or more doses of TG02 until improved to grade ≤ 1. If improved to grade ≤ 1 by Cycle 1 Day 1, initiate TMZ at initial dose and re-introduce TG02 at a reduced dose *.

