Second occurrence of grade 3 event with bleeding or grade 4 event occurring on Day -7 to Day -1 of cycle	
Skip one or more doses of TG02 until improved to grade ≤ 1. If improved to grade ≤ 1 by Cycle 1 Day 1, initiate TMZ at initial dose. Consider the individual benefit versus the risk of continuing TG02. If TG02 is re-introduced, re-introduce at a reduced dose *.
 
If TG02 has been re-introduced after a third event and the event recurs, discontinue TG02.

First occurrence of grade 3 event with bleeding or grade 4 event occurring on Day 1 to Day 7 of cycle	
Skip one or more doses of TG02 and interrupt TMZ until improved to grade ≤ 1. Consider the individual benefit versus the risk of continuing TMZ:
 
 • If TMZ is re-introduced, re-introduce TMZ and TG02 at a reduced dose *. • If TMZ is discontinued, continue TG02 at the same or a reduced dose * bi-weekly (on Days 1, 4, 8, 11, 15, 18, 22, 25) of a 28-day schedule.
Second occurrence of grade 3 event with bleeding or grade 4 event occurring on day 1 to Day 7 of cycle	
Skip one or more doses of TG02 and interrupt TMZ (if TMZ was re-introduced after the first event) until improved to grade ≤ 1. Re-introduce TG02 at a reduced dose *. Discontinue TMZ.
 
If TG02 has been re-introduced after a second event and the event recurs, consider the individual benefit versus the risk of continuing TG02. If TG02 is re-introduced, re-introduce at a reduced dose *.
 
If TG02 has been re-introduced after a third event and the event recurs, discontinue TG02.

Adverse Event	Action to be taken with TG02/ TMZ
Grade 3 or 4 event occurring on Day 21 – Day 28 of cycle	Skip one or more doses of TG02 and TMZ until improved to grade ≤ 1 . Re-introduce TG02 at initial dose and re-introduce TMZ at a reduced dose.
Recurrent grade 4 event occurring on Day 21 – Day 28 of cycle	Discontinue TMZ. Consider the individual benefit versus the risk of continuing TG02. If TG02 is continued, continue TG02 at the same or a reduced dose * bi-weekly (on Days 1, 4, 8, 11, 15, 18, 22, 25) of a 28-day schedule. Alternatively, discontinue TG02 and rechallenge with TMZ at lower dose.
Grade 3 or 4 event that does not improve to grade ≤ 2 within 28 days	Discontinue patient from study.
Anemia (TMZ decision as per local practice)	
First occurrence of grade 3 event	Skip one or more doses of TG02 until improved to grade ≤ 2 . Re-introduce TG02 at initial dose.

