Recurrence of the same grade 4 event	Discontinue TG02 and TMZ.

Group B: TG02-related Non-hematologic Adverse Events

Adverse Event	Action to be taken with TG02
Nausea / Vomiting (TMZ decision as per local practice)	
Grade 1 or 2 event	
Manage with moderate anti-emetic treatment until improved to grade ≤ 1. Prophylaxis should be given before TG02 dosing (see Section 5.6.2).
 
If a patient experiences persistent or recurrent grade 2 nausea/vomiting that do not improve to grade ≤ 1 with maximal supportive measures within 3 days, then TG02 dosing should be skipped until improved to grade ≤ 1. The dose of TG02 may be reduced *.

Grade 3 nausea Grade 3 or 4 vomiting	
Skip one or more doses of TG02 until improved to grade ≤ 1. If improved to grade ≤ 1 in <48 hours, re-introduce TG02 at the initial dose.
 
If not improved to grade ≤ 1 with maximal supportive measures within 48 hours, re-introduce TG02 at a reduced dose *.
 
Continue prophylaxis and management with at least moderate anti-emetic treatment (see Section 5.6.2).

Diarrhea (TMZ decision as per local practice)	
Grade 1 or 2 event	
Manage with anti-diarrheal treatment until improved to grade ≤ 1. Prophylaxis should be given before TG02 dosing (see Section 5.6.2).
 
If a patient experiences persistent or recurrent grade 2 diarrhea that does not improve to grade ≤ 1 with maximal supportive measures within 3 days, then TG02 dosing should be skipped until improved to grade ≤ 1. The dose of TG02 may be reduced *.
 
Continue prophylaxis and management with anti-diarrheal treatment (see Section 5.6.2).

Grade 3 or 4 event	
Skip one or more doses of TG02 until improved to grade ≤ 1. Physician should instruct patient regarding hydration. If improved to grade ≤ 1 in <48 hours, re-introduce TG02 at initial dose.
 
If not improved to grade ≤ 1 with maximal supportive measures within 48 hours, re-introduce TG02 at a reduced dose *.
 
Continue prophylaxis and management with anti-diarrheal treatment (see Section 5.6.2).

Cardiotoxicity	
Grade 3 event	
Discontinue TMZ.
 
Consider the individual benefit versus risk of continuing TG02. If TG02 is continued, continue TG02 at the same or a reduced dose * bi-weekly (on Days 1, 4, 8, 11, 15, 18, 22, 25) of a 28-day schedule.

Adverse Event	Action to be taken with TG02
Hepatotoxicity	

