First occurrence of grade 3 event	
Skip one or more doses of TG02 and interrupt TMZ until improved to grade ≤ 1. Re-introduce TG02 at a reduced dose *.
 
Consider the individual benefit versus the risk of continuing TMZ. If TMZ is re-introduced, re-introduce at a reduced dose.

Recurrence of the same grade 3 event	
If TMZ was re-introduced after the first event, discontinue TMZ. Skip one or more doses of TG02 until improved to grade ≤ 1. Consider the individual benefit versus the risk of continuing TG02. If TG02 is re-introduced, re-introduce at a reduced dose *.
 
If TG02 has been re-introduced after a second event and the event recurs, discontinue TG02.

First occurrence of grade 4 event	Discontinue TMZ. Skip one or more doses of TG02 until improved to grade ≤ 1 . Consider the individual benefit versus the risk of continuing TG02 at reduced dose *. If TG02 is re-introduced, re-introduce at a reduced dose *.
Recurrence of the same grade 4 event	Discontinue TG02.
Other non-hematologic events except alopecia and asymptomatic or reversible laboratory abnormalities	
First occurrence of grade 3 event	Skip one or more doses of TG02 and interrupt TMZ until improved to grade ≤ 1 . Provide appropriate symptomatic treatment. Re-introduce TG02 and TMZ at initial dose.
Second occurrence of the same grade 3 event	
Skip one or more doses of TG02 and interrupt TMZ until improved to grade ≤ 1. Provide appropriate symptomatic treatment. Re-introduce TG02 * and TMZ at a reduced dose.
 
If TG02 and TMZ have been re-introduced after a second event and the event recurs, discontinue TG02 and/ or TMZ.

First occurrence of the same grade 4 event	Skip one or more doses of TG02 and interrupt TMZ until improved to grade ≤ 1 . Provide appropriate symptomatic treatment. Re-introduce TG02 * and TMZ at a reduced dose.
Second occurrence of the same grade 4 event	
Skip one or more doses of TG02 and interrupt TMZ until improved to grade ≤ 1. Provide appropriate symptomatic treatment. Consider the individual benefit versus the risk of continuing TG02 and TMZ:
 
 • Discontinue TMZ. Continue TG02 at the same or a reduced dose * bi-weekly (on Days 1, 4, 8, 11, 15, 18, 22, 25) of a 28-day schedule. • Alternatively, discontinue TG02 and continue TMZ at a reduced dose.

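### Group B dose tables: the grade 3 cardiotoxicity row states no TG02 hold, and one thrombocytopenia branch allows an unchanged TG02 dose on twice as many days

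*Combined protocol and SAP*

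**What the plan says.** From cycle 2, Group B takes TG02 on days 1, 4, 22 and 25 of 28 (section 4.2). Cycle 1 lasts 35 days and adds doses on days -7 and -4 (section 6.2.2). Weeks 2 and 3 are left free because TG02 and TMZ may have overlapping toxicities (section 1.3.3.2). Only two TG02 levels exist, 150 and 100 mg. In all groups, a patient at 100 mg who needs a reduction comes off study treatment (section 5.5.3.1).

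**Cardiotoxicity, grade 3** (Group B non-hematologic table). TMZ is stopped and the investigator weighs benefit against risk. Then: "If TG02 is continued, continue TG02 at the same or a reduced dose", on days 1, 4, 8, 11, 15, 18, 22 and 25. The row does not say to wait for recovery. By contrast, the first grade 3 hepatotoxicity row in the same table opens with "Skip one or more doses of TG02 and interrupt TMZ until improved to grade" 1 or lower.

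**Thrombocytopenia, first event on Day 1 to 7, grade 3 with bleeding or grade 4** (Group B hematological table). Both drugs are held to grade 1 or lower. Two branches follow. In one, "If TMZ is re-introduced, re-introduce TMZ and TG02 at a reduced dose". In the other, "If TMZ is discontinued, continue TG02 at the same or a reduced dose", on the same eight-day schedule.

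**The concern.** A dose-modification table should give similar instructions after similar events, or show why they differ. In both cells, a patient who has just had a severe event can be moved to twice as many TG02 days at an unchanged dose. In the cardiotoxicity row this can happen while the event is unresolved. In the thrombocytopenia row it follows recovery, but neighbouring rules answer the same event with a TG02 reduction. At stake is the safety of elderly patients who are considered unfit for combined radiotherapy and TMZ, and consistent handling across sites.

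**Working it through.** No sample-size or error-rate figure applies. The check compares the rows and counts planned TG02.

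**1. Grade 3 cardiotoxicity against the other grade 3 non-hematologic rows**

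- Group B nausea/vomiting, diarrhea, hepatotoxicity and other events: TG02 skipped to grade 1 or lower (section 5.5.3.3.3).
- Groups A and C: neither has a cardiotoxicity row, so the other non-hematologic events row applies, and it also skips TG02 to grade 1 or lower (sections 5.5.3.2.2 and 5.5.3.4).
- Group B cardiotoxicity: no skip stated.
- Section 5.6.4.3 deals with QT/QTc prolongation only, and there it permits skipping without requiring it.

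The gap is the hold. On dose level the row is not more lenient, because Groups A and C resume at the initial dose after a first grade 3 event of this kind. The doubling of days is specific to Group B.

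**2. First thrombocytopenia of grade 3 with bleeding or grade 4**

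| Rule | TG02 after the hold |
|---|---|
| Group B, Day 1 to 7, TMZ stopped | same or reduced, 8 days |
| Group B, Day 1 to 7, TMZ resumed | reduced |
| Group B, second Day 1 to 7 event, TMZ stopped | reduced |
| Group A | reduced |
| Group C (TG02 alone) | reduced |

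The second-event row interrupts TMZ only if it had been resumed after the first event. It therefore also covers patients already on TG02 alone.

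**3. Planned TG02 per 28 days = dose x dosing days**

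- From 150 mg before the event (cycle 2 onward): 150 x 4 = 600 mg.
- TMZ stopped, same dose: 150 x 8 = 1200 mg; 1200/600 = 2.00.
- TMZ stopped, reduced dose: 100 x 8 = 800 mg; 800/600 = 1.33.
- TMZ resumed, reduced dose: 100 x 4 = 400 mg; 400/600 = 0.67.
- Group C and Group A maintenance after the same event: 100 x 8 = 800 mg; 1200/800 = 1.50.
- From 100 mg: 100 x 4 = 400 mg before, 100 x 8 = 800 mg after; 800/400 = 2.00.

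If the event falls in cycle 1, the comparison is six doses over 35 days: 150 x 6 = 900 mg, or 900/35 = 25.71 mg per day. The eight-day schedule gives 1200/28 = 42.86 mg per day, a ratio of 1.67.

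**4. How far the wording reaches**

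Seven Group B rows move TG02 to eight days at the same or a reduced dose once TMZ stops. In four of them (third grade 3 thrombocytopenia without bleeding, neutropenia, febrile neutropenia, second grade 4 other event) an earlier step has already required a reduction. That leaves three rows where 150 mg on eight days can be reached: the two cells above and recurrent grade 4 thrombocytopenia on Day 21 to 28. The last fits the stated TMZ profile, "For TMZ, a nadir occurs around day 21", and is not challenged.

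**The case against.** The best defence is that the thrombocytopenia rows follow attribution. Before Day 1, when only TG02 has been given, TG02 comes back reduced. Near the TMZ nadir, TMZ is cut and TG02 keeps its initial dose. On Day 1 to 7 both drugs are suspects, so either both are reduced or TMZ is removed for good. The four-day schedule exists because of overlap with TMZ, and 150 mg on eight days is simply the Group C regimen (section 4.3). The row holds both drugs first, the investigator may choose the reduced dose, and a second event requires it.

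Most of this stands and keeps the point small. It explains the change of schedule. It does not explain the unchanged dose: Group C has no TMZ in its regimen and still reduces, and so does the second-event row for patients already off TMZ.

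For cardiotoxicity, the investigator can decline to continue TG02, section 5.4 stops treatment for unacceptable toxicity, and section 5.5.3.1 refers uncertainty to the sponsor. None of these states a hold, and section 5.5.3.3.2 allows skipped doses as the tables describe, so the table is where the hold belongs.

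A reader might go further and infer that a Day 1 to 7 event points to TG02, because of TG02 thrombocytopenia the protocol says: "Onset was typically within the first week of administration and resolved within 72 hours after TG02 interruption". The documents do not support that. In cycle 1, TG02 starts on Day -7, so Day 1 to 7 is its second week. In later cycles these days follow TG02 on days 22 and 25 and the previous TMZ nadir, and TMZ is itself given on days 1 to 5. The onset statement also comes from 250 mg with carfilzomib.

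**Conclusion.** Both points hold as a minor, inexpensive patient-safety improvement. As written, the cardiotoxicity row permits twice the TG02 days during unresolved grade 3 cardiotoxicity. The thrombocytopenia branch permits 1200 mg per 28 days from 150 mg, which is 2.00 times the cycle 2 schedule and 1.50 times the amount in Group C after the same event. These figures are planned doses with no further skips, and they assume the investigator keeps the dose unchanged, which is allowed but not required.

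Two further inferences are not supported. One is that patients would be harmed: the documents give no evidence of harm and no frequency for either branch. The other is that Group B's dose finding or safety reporting is compromised. The MTD rests on cycle 1 DLTs, and this platelet event in cycle 1, if judged clinically significant and possibly treatment-related, is a DLT whatever dosing follows (section 5.2.1.2). Although section 8.2.2 uses one safety population, section 7.3.2 already has the highest grade computed per cycle and per patient, so later cycles on TG02 alone can be identified.

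**What to change.** 1. In the Group B grade 3 cardiotoxicity row, add that TG02 is skipped until the event is grade 1 or lower before any resumption. The 28-day limit in section 5.5.3.1 then applies as it does elsewhere.
2. In the TMZ-stopped branch of the first Day 1 to 7 thrombocytopenia row, require 150 mg to become 100 mg when TG02 moves to eight days. The result is 800 mg per 28 days, still 1.33 times the earlier 600 mg but equal to Group C and Group A maintenance after the same event.

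For patients already at 100 mg, section 5.5.3.1 (all groups) points to stopping, while section 5.5.3.3.2 says TG02 can continue when TMZ has to be discontinued. That is a clinical trade-off for the medical team and is not part of the two edits.

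A table of adverse events before and after the switch is optional. Counts would be sparse with at most 12 evaluable patients.

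Cost: two table cells at the next amendment, and a lower TG02 dose or a short delay for patients who enter these branches.

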5.5.3 TG02

5.5.3.1 For all groups

The following dose levels of TG02 will/can be used:

- 150 mg (groups A,B,C)
- 100 mg (groups A,B, C)

TG02 dose should not be reduced below 100 mg. If a patient's initial or current dose is 100 mg and the patient experiences a toxicity requiring TG02 dose reduction as described in the tables below, the patient should be discontinued from study treatment.

TG02 should not be skipped for more than 28 days. If TG02 cannot be re-introduced within 28 days, the patient should be discontinued from the study treatment.

In case of uncertainty regarding dose modifications described in the tables below, please contact the Sponsor.

In all cases, appropriate symptomatic treatment should be considered to manage the AE.

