5.5.3.3 Group B

5.5.3.3.1 Dose escalation phase

Cycle 1: no TG02 or TMZ dose reductions are allowed in Cycle 1 except if a patient experiences a DLT.

Skipped doses of TG02 are allowed. A "skipped dose" for TG02 when TMZ is not interrupted means that one or more single doses will be omitted and not replaced, in order not to change the temporal relationship with TMZ.

For example, if TG02 is planned on days 1, 4 and 22, but day 4 has to be omitted, TG02 can be restarted on day 22 if the AE is sufficiently resolved: TG02 is always restarted on a scheduled dose day.

Interruptions of TMZ are allowed.

Skipping TG02 or interrupting TMZ for >25% of the planned total dose in Cycle 1 will be considered a DLT (see section 5.5.1).

Toxicities possibly related to TG02 should be managed as outlined in the tables below. Toxicities of TMZ should be managed as outlined in the table below and per local practice, where noted.

Cycles 2+: TG02 dose reductions and skipped dose(s) can be made for adverse events as described in the tables below. TMZ dose reductions and interruptions can be made for adverse events as described in section 5.5.2 and the tables below.

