5.5.3.3.2 Expansion phase

TG02 dose reductions and skipped dose(s) are allowed in any cycle as described in the tables below. A "skipped dose" for TG02 when TMZ is not interrupted means that one or more single doses will be omitted and not replaced, in order not to change the temporal relationship with TMZ.

For example, if TG02 is planned on days 1, 4 and 22, but day 4 has to be omitted, TG02 can be restarted on day 22 if the AE is sufficiently resolved: TG02 is always restarted on a scheduled dose day.

Toxicities possibly related to TG02 should be managed as outlined in the tables below. Toxicities of TMZ should be managed as outlined in the table below and per local practice, where noted.

In the absence of progressive disease, either TMZ or TG02 may be interrupted/ skipped or discontinued permanently while treatment with the other agent is continued. In all cases where TMZ has to be discontinued, patient can continue with TG02. Otherwise patient is considered off study and treating physician can consider other treatment such as RT.

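### Group B thrombocytopenia table: a grade 3 event without bleeding on Days 21 to 28 meets two rows with different restart doses, and no rule says which governs (minor, patient safety)

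*Combined protocol and SAP*

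**What the plan says.** All rows below are in the thrombocytopenia part of the Group B table in section 5.5.3.3.3.

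- First grade 3 event without bleeding, no day stated: hold both drugs until grade 1 or less, then "Re-introduce TG02 and TMZ at initial dose".
- Recurrent grade 3 event without bleeding, no day stated: same hold, then "Re-introduce TG02 at a reduced dose * and TMZ at a reduced dose".
- A row labelled "Grade 3 or 4 event occurring on Day 21" to Day 28, with no mention of bleeding or of first versus recurrent: same hold, then "Re-introduce TG02 at initial dose and re-introduce TMZ at a reduced dose".
- One recurrence row for that window, limited to grade 4: "Recurrent grade 4 event occurring on Day 21" to Day 28. It stops TMZ, with a choice about TG02, or stops TG02 and rechallenges with TMZ at a lower dose.

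Section 5.5.3.1 sets 100 mg as the lowest TG02 dose. For a patient whose initial or current dose is 100 mg, it says that if "the patient experiences a toxicity requiring TG02 dose reduction as described in the tables below, the patient should be discontinued from study treatment". Under the expansion phase, section 5.5.3.3.2 adds that, without progression, "either TMZ or TG02 may be interrupted/ skipped or discontinued permanently while treatment with the other agent is continued".

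The tables are binding on sites. Section 5.5.3.3.1 states "Cycles 2+: TG02 dose reductions and skipped dose(s) can be made for adverse events as described in the tables below", and section 5.5.3.3.2 applies them in any cycle of the expansion phase. Section 5.5.2 makes local TMZ practice give way to them.

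**The concern.** A row defined by bleeding status and a row defined by day of cycle can both describe the same event. When they give different doses and nothing ranks them, two sites that each follow a matching row can treat the same patient differently without either departing from the protocol. The population is over 65, and section 5.2.1.2 expects TG02 and TMZ to overlap in hematological toxicity. For a patient at 100 mg with a recurrence, one row means stopping TG02 and the other means giving it again.

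**Working it through.** No sample size or error rate is involved, so the check sets the rows side by side for one event type: grade 3 thrombocytopenia, no bleeding, Days 21 to 28.

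| Occurrence | Drug | Any-day row | Day 21 to 28 row | Result |
|---|---|---|---|---|
| First | TG02 | initial | initial | agree |
| First | TMZ | initial | reduced | **conflict** |
| Recurrent | TG02 | reduced | initial | **conflict** |
| Recurrent | TMZ | reduced | reduced | agree |

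One drug conflicts in each case. Neighbouring rows do write out the limit to grade 3 with bleeding or grade 4, so its absence from the Day 21 to 28 row cannot be read as implied.

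**Possible tie-breakers**
- Local TMZ practice (5.5.2) yields to the tables.
- The ban on reductions in Cycle 1 of the escalation phase (5.5.3.3.1) does not choose between the rows for TMZ, because interrupted TMZ restarts only at the next cycle (5.5.2), when reductions are allowed.
- Section 5.5.3.1 tells sites to contact the Sponsor when uncertain. That helps a site that sees both rows, but not one that stops at the first match.
- The case-by-case guidance in the table's preamble concerns attribution to TMZ or TG02, not precedence between rows.

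**Size of each conflict**
- First event: planned TMZ at the initial dose is 5 × 200 = 1000 mg/m² per cycle, against a reduced dose that the table does not quantify.
- Recurrence at 150 mg: from Cycle 2, TG02 is planned on Days 1, 4, 22 and 25 (section 4.2). That is 4 × 150 = 600 mg under the Day 21 to 28 row and 4 × 100 = 400 mg under the any-day row, a difference of 200/600 = 33%.
- Recurrence at 100 mg: 4 × 100 = 400 mg, or TG02 stopped. In the expansion phase TMZ may continue alone. The first Group B cohort is three patients at 100 mg (5.2.1.2), so this applies from the start.

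**Reach**
- Section 6.2.2.2 schedules Cycle 1 counts on Days 1, 8, 15 and 22, so Day 22 falls in the window. From Cycle 2 the count belongs to the Day 1 visit, plus or minus 3 days (6.2.4); an early visit can be read as Day 1 of the next cycle, outside the window.
- A recurrence found on Cycle 1 Day 22 would need an earlier grade 3 event and recovery within the same cycle. The TG02 conflict therefore depends mainly on unscheduled counts or on how an early visit is labelled.
- The documents give no event rate for this regimen. The table in 5.2.1.2 covers 12 patients on TG02 200 or 250 mg with TMZ on a different schedule: thrombocytopenia in 6, no grade 3 or 4 entry. The Group B table's preamble cites 21% grade 3 or 4 at TG02 250 mg with carfilzomib. Taking 0 to 21% as an assumed range for 12 patients gives 0 to 12 × 0.21 ≈ 2.5 patients with any grade 3 or 4 event. Fewer would have one that is both without bleeding and in the window.

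**The case against.** The strongest reply is that one natural reading settles everything. The preamble places the TMZ nadir around day 21, and TG02-related onset, in the carfilzomib study, typically in the first week of administration. The Day 21 to 28 row follows that logic by reducing TMZ and keeping TG02. It has no first-occurrence limit, whereas the Day -7 and Day 1 to 7 rows separate first from second events. On this reading it covers every grade 3 event in the window.

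That reading is reasonable, especially for first events, but it is written nowhere. For a recurrence it is weaker: the any-day row is specific on occurrence and bleeding, the other on day, so specificity does not pick a winner.

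The safeguards also count. Beyond Sponsor contact, section 18.1 calls for a teleconference at the end of each escalation cohort, and section 9.2.1 provides regular medical review of safety and treatment compliance. These limit how long a divergence would go unnoticed. They do not make the instruction unambiguous when the site has to act.

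A reader might infer that the table allows dosing through unresolved toxicity. It does not: both rows hold both drugs until grade 1 or less. A reader might also measure the problem by the share of cycle days in the window. Calendar share is not opportunity to detect an event, and only one scheduled count clearly falls there.

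**Conclusion.** The table is wrong as written, as a minor patient-safety matter. Two stated dosing rules contradict each other for one identifiable event: on TMZ at a first occurrence, and on TG02 at a recurrence, with stop versus restart at 100 mg. This rests on reading the row labels as printed, and on 100 mg being the only reduction step from 150 mg (5.5.3.1).

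The effect is small: at most 12 evaluable patients, no event rate for the regimen, and one scheduled count clearly in the window. A reader might infer that dose finding is compromised. The documents do not support that: section 5.2.1.2 defines DLT and MTD without reference to the restart rows, the two rows hold treatment identically, and no planned analysis depends on which row is used. Nor does the 100 mg rule always end all treatment, since in the expansion phase TMZ may continue alone.

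**What to change.** Edit the thrombocytopenia rows in three linked steps.

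1. Relabel the Day 21 to 28 row as first occurrence of a grade 3 or 4 event, and state that it overrides the any-day first-occurrence row in that window. This fits the TMZ nadir.
2. State that the any-day recurrence row governs recurrent grade 3 without bleeding, including on Days 21 to 28.
3. Widen the Day 21 to 28 recurrence row from grade 4 to grade 3 with bleeding or grade 4.

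Step 3 matters. Settling only the non-bleeding events would leave recurrent bleeding grade 3 in the window restarting TG02 at the initial dose, while the milder recurrence is reduced or stopped. A bleeding event should never draw the milder action. Because the widened row can let TG02 continue at the same dose once TMZ stops, the clinical team should confirm that option for patients at 100 mg.

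If the team instead wants the Day 21 to 28 row to govern every grade 3 event in the window, it should say so and limit the any-day rows to days outside it. The choice of action is clinical; the protocol needs to state one.

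The cost is a table correction in the next amendment and a notice to sites, with no extra visits or tests.
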